4.1 Main Study Objective

The main objective of our study is to determine if treatment with sirolimus can improve clinical outcomes in hospitalized patients with COVID-19.

4.2 Primary Endpoint:

Progression to respiratory failure requiring advanced support measures, either due to inadequate ventilation (non-invasive or invasive mechanical ventilation) or inadequate oxygenation (CPAP* or high flow supplemental oxygen at rates \geq 15 liters/minute), in patients given sirolimus compared to the placebo group.

4.3 Secondary Endpoints:

Key secondary endpoints:

- Escalation in level of care
- Increase in total lymphocyte count
- Normalization of biomarkers (Ferritin, LDH, and d-dimer)
- Survival to hospital discharge
- Drug safety profile (Incidence and type of adverse and serious adverse events)

Other outcomes measures:

- Fever
- Duration of advanced respiratory support
- Duration of hospital stay (in survivors)
- Time from treatment initiation to death (in non-survivors)
- Need for initiation of other off-label rescue therapies such as Anti IL-6 agents, at the discretion of treating clinicians

* CPAP use for known obstructive sleep apnea will not be considered as disease progression.

5. Study Design

We will employ a randomized, double blind, placebo-controlled study design. 30 patients hospitalized with COVID-19 and meeting the inclusion criteria specified below will be randomized to receive sirolimus or placebo in a 2:1 manner. The treatment regimen and duration are provided in Sections 5.5 and 5.6.

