The vast majority of the common side effects (e.g. hyperlipidemia, increased risk of malignancies) are of concern with prolonged/long-term use of sirolimus. Since our study duration is limited to 14 days, these measurements may not be of significant concern. Side effects of particular interest given the nature of this study will be incidence of secondary infections and other organ system toxicities (pneumonitis, increased serum creatinine, decreased blood counts). We will carefully monitor for all laboratory abnormalities at baseline and on days 3, 7, and 14. We will also enquire about any possible AEs from the patients at days 1, 3, 7, and 14.

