14.3.4 Adverse events associated with laboratory testing

The following table highlights the laboratory values that are being obtained as part of the study along with the reference range for normal values. While any value outside the reference range will be classified as abnormal, the clinical significance of those abnormal values will be determined based on the criteria set forth in the table. All lab values identified as clinically significant will be marked as an AE. The causality and attribution of the lab value to the study drug, as well as action items with regards to follow-up and management of laboratory values that are listed as clinically significant, will be adjudicated on an individual basis by the study PI.

Laboratory parameter	Reference Range	Reported as clinically significant if
Serum Creatinine	0.50 – 0.99 mg/dl	≥1.5 times baseline
AST	10 – 35 U/L	≥ 105 U/L (3 times ULN)
ALT	6 – 29 U/L	≥ 87 U/L (3 times ULN)
Hemoglobin	11.7 – 15.5 gm/dl	Decrease of ≥2gm/dL from baseline
Total white blood cells	3.8 – 10.8 x 10 ³ /µL	≤ 3 or ≥ 11.5 x 10 ³ /µL
Absolute neutrophils	1500 – 7800 cells/µL	< 1,000 or > 9,500 cells/µL
Absolute lymphocytes	850 – 3900 cells/µL	< 500 or > 4500 cells/µL
Absolute monocytes	200 – 950 cells/µL	< 150 or > 1,500 cells/µL
Absolute eosinophils	15 – 500 cells/µL	< 5 or > 1,000 cells/µL
Absolute basophils	0 – 200 cells/µL	> 500 cells/µL
Platelet count	140 – 400 x 10 ³ /µL	< 120 or > 450 x 10 ³ /µL

Abbreviations: AST = Aspartate aminotransferase, ALT = Alanine aminotransferase, MCH = Mean corpuscular hemoglobin, MCHC = Mean corpuscular hemoglobin concentration, MCV = Mean corpuscular volume, RDW = Red blood cell distribution width.

While the guidance above is meant to cover all laboratory values obtained during the study, we realize that it may not be able to cover all the unique circumstances that can arise during the conduct of a clinical trial. As such, in rare situations, the study PI may change the clinical significance of a lab value outside of the above guidance. We do not anticipate this situation to arise commonly, however, and if deviating from the above range while assigning clinical significance, the reason for this diversion will be clearly outlined in the subject's study binder. Adverse events related to study medication will be tabulated by body system and by severity using the NCI CTCAE v 5.0.

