14.4.2 Recording AEs

Throughout the study all identified AEs (serious and non-serious) will be recorded on all appropriate source document and AE case report forms (CRFs) regardless of their severity or relation to the study. A complete description of all AEs will include event description, time of onset, investigator assessment of severity, relationship to study agent or procedures, time of resolution/stabilization of the event, expectedness, determination of whether the AE qualifies as a SAE, and action taken. A change in the severity of the AE will also be documented.

Assessment of severity and relationship will be documented on the source documents or on the CRFs.

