14.5 Managing adverse events

The study investigator must apply his or her clinical judgment as to whether an AE is of sufficient severity to require that the participant immediately be removed from further receiving

the study agent under the protocol. The investigator must institute any necessary medical therapy to protect a participant from any immediate dangers.

An AE will be followed until any of the following takes place: a) it is resolved, b) participant is stable, c) participant is discharged from the hospital and the PI determines that follow-up is no longer needed.

If an abnormal value or result from a clinical or laboratory evaluation is determined to be an AE, then the evaluation that produced the value or result can be repeated until the value or result returns to normal, or the result can be explained, or the usual standard of care does not require further follow-up, and the participant's safety is not at risk.

Non-serious expected AEs will be submitted to the DSMB in a timely fashion. The events will be presented in tabular form and given to the DSMB at every scheduled meeting. Study investigators are also required to fulfill all reporting requirements of their local institutions.

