For additional information and a printable version of the NCI-CTCAE manual, the NCI-CTCAE website: <http://ctep.cancer.gov/reporting/ctc.html> will be consulted. In a clinical trial, the study product/intervention will always be suspect when attributing an AE and the "unrelated" attribution will be used only when there is an undisputable or likely alternative explanation for the AE.

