14.10 Non-serious adverse events reporting

14.10.1 Notifying the data and safety monitoring board

The DSMB will be notified of non-serious AEs during their regularly scheduled meetings. The events will be presented to the Board in tabular format.

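### The one adverse-event table specified by body system and severity is limited to events judged drug-related, which is narrower than the all-event safety endpoint, and the SAP specifies no all-cause comparison by arm

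*Combined protocol and SAP*

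**What the plan says.** The key secondary endpoints in protocol section 4.3 include "Drug safety profile (Incidence and type of adverse and serious adverse events"), with no restriction to drug-related events. Section 14.4.2 requires all AEs to be entered on "case report forms (CRFs) regardless of their severity or relation to the study". Section 14.3.4, which otherwise deals with laboratory values, closes with the tabulation rule: "Adverse events related to study medication will be tabulated by body system and by severity using the NCI CTCAE v 5.0".

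Section 9.1 singles out what the investigators most want to watch: "Side effects of particular interest given the nature of this study will be incidence of secondary infections", followed by pneumonitis, raised creatinine and reduced blood counts.

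Under section 14.7, the PI or a designated physician assigns attribution on a five-point scale. Unrelated and Unlikely form the unrelated category; Possible, Probable and Definite are the related categories. The study product is always to be suspected, and the unrelated attribution is reserved for cases "when there is an undisputable or likely alternative explanation for the AE".

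Protocol section 15 and the SAP cover sample size, the primary endpoint, randomisation and exploratory analyses. Neither describes any analysis of AEs.

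**The concern.** In a randomised placebo-controlled trial, background disease and concomitant drugs act in both arms, so event rates can be compared without anyone deciding what caused each event. A table filtered on attribution gives up that advantage.

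The filter matters here because the events of particular interest in section 9.1 have ready alternative explanations. Section 3.2 reports lymphopenia in 60-80% of hospitalised COVID-19 patients, section 4.3 anticipates anti-IL-6 rescue, and the SAP anticipates corticosteroid use. An infection or a low count may reasonably be judged more likely due to one of these than to study drug.

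At stake is the final safety summary of a 30-patient pilot meant to inform a larger trial. If the stated rule is followed and nothing is added, the summary answers a narrower question than the endpoint asks. An excess on sirolimus could then look smaller than it was.

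**Working it through.** **Step 1. Which AE outputs are stated, and what each covers.** The plan gives no figure for the AE analysis to reproduce, so the main check is of the text.

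| Place | Events covered | Layout stated | Comparison by arm stated? |
|---|---|---|---|
| 4.3, endpoint | All AEs and SAEs | None | No |
| 14.3.4, table | Related AEs only | Body system and severity | No |
| 14.5, DSMB table | Non-serious expected AEs | Tabular only | No |
| 14.10.1, DSMB table | Non-serious AEs | Tabular only | No |
| 14.1, DSMB review | All AEs, patterns and frequencies | None | Unblinded review, no table defined |
| 14.1, aggregate report | Not limited to related events | Severity, attribution, relationship | No |
| 14.3.5, SAE reporting | SAEs whatever the relationship | Event reports | No |
| 14.8.2, IND annual report | All AEs | None | No |
| Section 15 and SAP | No AE analysis | None | No |

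Three things follow. The 14.3.4 table is the only one specified by body system and severity, and it is narrower than the endpoint. The two DSMB tables have no relatedness limit, but they cover non-serious events only. No output is described as an end-of-study all-cause comparison by arm.

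**Step 2. What the filter removes.** Reading related as the related categories of section 14.7, codes 3 to 5 stay in the table and codes 1 and 2 drop out. Possible is code 3 and stays even when another cause exists. The loss is therefore confined to events for which the assessor thinks the other cause likely or certain. Section 14.3.4 does not itself tie related to those codes, and section 14.8.1 words the causality categories differently, so the boundary also needs stating.

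**Step 3. Illustration of size.** All rates below are assumptions, because the documents give no AE rates by arm and no share coded related. The only design input is 30 patients at 2:1: 30 × 2/3 = 20 sirolimus and 30 × 1/3 = 10 placebo.

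Let pS and pP be the true event rates and f the share of events coded related, taken as equal in both arms. Then:

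- tabulated rate = f × true rate
- tabulated difference = f × (pS − pP)
- chance that the sirolimus column is empty = (1 − f × pS)^20

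With 6/20 = 30% against 1/10 = 10%, the true difference is 20 points. At f = 1/3 the table shows 10% against 3.3%, a difference of 6.7 points. At f = 1 it shows the full 20 points.

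With 30% against 15%:

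| f | Expected sirolimus events (of 20) | Expected placebo events (of 10) | Difference, points | Chance of empty sirolimus column |
|---|---|---|---|---|
| 1 | 6.0 | 1.5 | 15 | 0.1% |
| 0.75 | 4.5 | 1.1 | 11 | 0.6% |
| 0.5 | 3.0 | 0.75 | 7.5 | 3.9% |
| 0.25 | 1.5 | 0.4 | 3.75 | 21% |

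For a rarer event, 10% against 5%, the chance of an empty sirolimus column rises from (1 − 0.10)^20 = 12% at f = 1 to (1 − 0.025)^20 = 60% at f = 0.25.

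With f equal in both arms the ratio of rates is unchanged. What shrinks is the counts and the absolute difference, which is what a reader of a 20-against-10 table sees.

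**The case against.** The strongest reply is that the information exists and is looked at. "The DSMB will be notified of non-serious AEs during their regularly scheduled meetings", and "The events will be presented to the Board in tabular format", with no relatedness limit. Section 14.5 adds, for non-serious expected events: "The events will be presented in tabular form and given to the DSMB at every scheduled meeting". The expected list in section 14.3.6 includes infections, pneumonitis, anaemia, thrombocytopenia and raised creatinine, which are largely the events at issue. The DSMB reviews all AEs unblinded at 25%, 50%, 75% and 100% of enrolment. The 14.3.4 sentence also does not say that only related events will be tabulated.

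This stands as far as it goes. It disposes of a tempting stronger reading, that 14.3.4 is the only AE table in the plan and that events would vanish from the trial's safety assessment. It does not supply a final comparison: those outputs serve oversight and regulatory reporting, and the two DSMB tables leave out serious events.

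The second reply is that the attribution rule leans towards keeping events, since the product is always suspect and Possible counts as related. That also stands. It limits the loss to Unlikely and Unrelated events but does not remove it.

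A reader might also infer that attributions are made with the allocation known, because sections 6.1, 7.1 and 12.3.2 allow unblinding at deterioration. The documents do not support this. Unblinding there is case by case, on the treating clinician's judgement, while attribution belongs to the PI or designee. Nothing says the assessor learns the allocation or attributes events after the code is broken.

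Finally, the numbers in the illustration are assumed, and even the unfiltered 6/20 against 1/10 gives a two-sided Fisher p of about 0.37. The example shows how the filter shrinks a difference; it does not show that a safety conclusion would change.

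**Conclusion.** The point holds as a gap in how safety results are specified. The one AE table defined by body system and severity covers related events only, the endpoint covers all AEs and SAEs, and the SAP provides no all-cause comparison by arm. Events coded Unlikely or Unrelated would be missing from that table, and they may include the infections and organ toxicities named in section 9.1.

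The size cannot be determined from the documents. Under the assumed 30% against 10%, the tabulated excess runs from 6.7 points (one third coded related) to 20 points (all coded related), given equal coding shares in both arms. The upper end is no loss at all.

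The data remain available and the DSMB sees them during the trial, so the gap can be closed fully at analysis. It should be closed in the plan, before results are known, so that the choice of table cannot depend on them.

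**What to change.** Replace the closing sentence of section 14.3.4, and add the same text to the SAP:

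*All adverse events and all SAEs occurring after the first dose will be tabulated by arm, body system and highest CTCAE grade, irrespective of attribution; related events will be shown as a subset.*

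Three details go with it:

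- Separate rows for the section 9.1 events of interest: secondary infection, pneumonitis, increased serum creatinine and decreased blood counts.
- A statement that related means Possible, Probable or Definite as in section 14.7, with the category names in section 14.8.1 brought into line.
- The same layout for the unblinded DSMB tables, with SAEs included, so that interim and final summaries can be read together.

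The cost is a short text change and one more table. All AEs are already recorded with severity and relationship under section 14.4.2, so there is no new data collection and no added burden on patients.

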14.3.5 Serious Adverse Event (SAE)

An AE or SAR is considered "serious" if it results in any of the following outcomes (21 CFR 312.32(a)):

- Death: A death that occurs during the study or that comes to the attention of the investigator during the protocol-defined follow-up.
- A life-threatening event: An AE or SAR is considered "life-threatening" if, in the opinion of the investigator, its occurrence places the subject at immediate risk of death. It does not include an AE or SAR that, had it occurred in a more severe form, might have caused death.
- An inpatient hospitalization or prolongation of existing hospitalization.
- Persistent or significant disability/incapacity or substantial disruption of the ability to conduct normal life functions.
- An important medical event that may not result in death, be life threatening, or require hospitalization may be considered an SAE when, in the opinion of the investigator, it may jeopardize the participant and may require medical or surgical intervention to prevent one of the outcomes listed above.
- Congenital anomaly or birth defect.

Regardless of the relationship of the AE to the study, the event will be reported per Section 14.3.5 as an SAE if it meets any of the above definitions.

14.3.6 Expected adverse events

Detailed information regarding adverse effects of sirolimus is provided in Section 9.1. This section lists the AEs regarded as expected for sirolimus (in alphabetical order of systems):

Cardiovascular: Peripheral edema, hypertension

Cutaneous: Acne, skin rash, mucositis

Gastrointestinal: Nausea, vomiting, diarrhea, constipation, dyspepsia

General: Fatigue, myalgias, arthralgias

Hematological: Anemia, thrombocytopenia

Infectious: Increased risk of infections

Liver: Increased serum bilirubin

Nervous system: headache
Pulmonary: pneumonitis
Renal: Increased serum creatinine

14.3.7 Unexpected adverse event

An AE or SAR is considered “unexpected” when its nature, severity or frequency is not consistent with the information that is provided with the information in the protocol.

14.4 Collecting, recording and managing adverse events

14.4.1 Identifying adverse events

Any AE that occurs from the moment the subject has signed the consent form will be recorded and is reportable. Collection time for AEs and SAEs will begin after the screening visit when the consent form is signed and will continue until the end of the treatment.

Adverse events may be discovered through any of these methods:

- Electronic medical record review
- Observing the participant
- Questioning the participant, with standardized questions/procedures.
- Receiving an unsolicited complaint from the participant.
- An abnormal value or result from a clinical or laboratory evaluation can also indicate an AE when determined to be clinically significant by the PI. Pre-specified criteria for abnormal lab values are provided in Section 14.3.4.

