Exclusion Criteria	
Subjects who meet ANY of the following criteria are not eligible for enrollment as study participants:
 
 Known allergy or hypersensitivity to sirolimus Inability or refusal to provide informed consent Advanced respiratory support (high flow oxygen ≥ 15 L/min, CPAP, non-invasive or invasive mechanical ventilation) Active enrollment in other interventional clinical drug trials. Co-enrollment in observational studies and biorepositories is allowed. Pregnant women Breast feeding On chronic immunosuppression for other medical conditions such as rheumatological disorders, inflammatory bowel disease, or in patients with organ transplants. A list of these medications is provided in Section 12.3.4 Any clinically significant medical disease which in the opinion of the investigator precludes the patient from enrolling in the trial, including (but not limited to): 
 History of liver cirrhosis End stage renal disease or need for renal replacement therapy Decompensated heart failure Known active tuberculosis or history of incompletely treated tuberculosis Uncontrolled systemic bacterial or fungal infections Active viral infection other than COVID-19

	
 ○ Lymphoma or other systemic malignancies, either current or treated within the past 2 years. Localized non-melanoma skin cancer is not an exclusion.
Study Overview	
The main objective of our study is to determine if treatment with sirolimus can improve clinical outcomes in hospitalized patients with COVID-19. We will employ a randomized, double blind, placebo-controlled study design. 30 subjects will be randomized in a 2:1 fashion to receive sirolimus or placebo. Sirolimus will be given as a 6mg oral loading dose on day 1 followed by 2mg daily for a maximum treatment duration of 14 days or until hospital discharge, whichever happens sooner. Chart reviews will be conducted daily to determine changes in clinical status, concomitant medications and laboratory parameters. Study specific biomarkers will be measured at baseline and then at days 3, 7 and 14.

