6.1 Study and Timeline Overview

Patients will be identified by the medical and research staff at the University of Cincinnati Medical Center and the facilities of the affiliated health systems UC Health, LLC and University of Cincinnati Physicians Company, LLC. Recruitment will take place until 30 evaluable patients have been enrolled, or the incidence of new cases does not permit further enrollment. Patients who meet eligibility criteria, provide informed consent and are enrolled in the study will receive instructions regarding study drug dosage, route and administration. The study drug will be given each morning along with other inpatient medications at roughly the same time every day. Patients will be on the study drug for a maximum duration of 14 days, or until hospital discharge, whatever happens first. In case a patient progresses to require advanced respiratory support, the study drug can continue as scheduled at the discretion of the treating clinician(s). If deemed clinically necessary on a case-by-case basis, in these scenarios the patient may need to be withdrawn ± unblinded.

All study procedures will take place after obtaining informed consent. Details of the informed consent process are provided in Section 6.3. Prior to starting study drug, baseline demographic and clinical variables will be collected along with vital signs, amount of supplemental oxygen required, laboratory biomarkers such as absolute lymphocyte count, ferritin, LDH, and d-dimer, renal and liver function tests, concomitant medications, past medical history, and results of the chest imaging. After study initiation, chart reviews will be conducted on a daily basis to assess vital signs, changes to concomitant medications, lab values, and oxygenation indices. Study-specific biomarkers: absolute lymphocyte count, serum ferritin, d-dimer and LDH will be measured at Day 3, 7 and 14 following study initiation, unless already checked clinically in the 24 hours prior to the testing time.

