6.2 Schedule of Events

Event	Screening ¹	D1	D2	D3	D4	D5	D6	D7	D8	D9	D10	D11	D12	D13	D14 ⁶	F/u ⁷
Informed consent	X															
Demographics	X															
Medical history	X															
Determine study eligibility	X															
Con meds	X	X	X	X	X	X	X	X	X	X	X	X	X	X	X	
Review AEs			X				X								X	
Heart rate/pulse ²	X	X	X	X	X	X	X	X	X	X	X	X	X	X	X	
MAP ²	X	X	X	X	X	X	X	X	X	X	X	X	X	X	X	
Highest daily temperature (F)	X	X	X	X	X	X	X	X	X	X	X	X	X	X	X	
Oxygen saturation ²	X	X	X	X	X	X	X	X	X	X	X	X	X	X	X	
FiO ₂ (%) ^{2, 3}	X	X	X	X	X	X	X	X	X	X	X	X	X	X	X	
Pregnancy test ⁴	X															
LDH ⁵	X			X				X							X	
Ferritin ⁵	X			X				X							X	
D-dimer ⁵	X			X				X							X	
Absolute lymphocytes ⁵	X			X				X							X	
CBC (WBCs, Hb, Platelets) ⁵	X			X				X							X	
Serum creatinine ⁵	X			X				X							X	
AST, ALT ⁵	X			X				X							X	
Advanced resp. support (Y/N)	X	X	X	X	X	X	X	X	X	X	X	X	X	X	X	
Vital status	X	X	X	X	X	X	X	X	X	X	X	X	X	X	X	

¹ Screening visit can be the initial visit if a patient meets all inclusion/exclusion criteria

² Mean recorded value for the 24-hour duration of that day

³ FiO₂ (%) will be recorded if directly available from chart review such as in patients on ultra-high flow devices (vapotherm, optiflow etc.) or in patients on advanced respiratory support. For all other patients, FiO₂ (%) will be calculated based on the following conversion:

Supplemental O ₂ (l/min)	0	1	2	3	4	5	6	7	8	9	10	11	12	13	14
FiO ₂ (%)	21	24	27	30	33	36	39	42	45	48	51	54	57	60	63

⁴ Only required for women of childbearing potential, if not already obtained clinically

⁵ No need to recheck if already drawn clinically in the 24 hours prior to the study-specified time. If not checked clinically, these can be measured as research tests. If COVID-19 biorepository sample obtained on the day of these tests, they can be postponed to the next day.

⁶ In case a patient is discharged from the hospital before the 14-day period, their last hospital day will be treated similar to Day 14 with regards to study assessments

⁷ Long term outcomes following the 14-day study period will be assessed by chart reviews

Abbreviations: AE = adverse event, ALT = Alanine aminotransferase, AST = Aspartate aminotransferase, CBC = complete blood count, F = degrees Fahrenheit, FiO₂ = Fraction of inspired oxygen, Hb = Hemoglobin, LDH = Lactate dehydrogenase, MAP = Mean arterial pressure, WBCs = White blood cells

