- Query the patient with regards to any adverse effects from the study medication. This can be done remotely via telephone interview rather than in-person visit in order to minimize study staff exposure as well as preserve PPE

In case a subject is discharged from the hospital before Day 14, every effort will be made to complete the day 14 activities on the day of hospital discharge. In case the duration of hospitalization extends beyond the study duration of 14 days, we will periodically monitor the electronic medical record and record key variables such as the need for advanced respiratory support, duration of hospitalization, duration of ICU status, time spent on mechanical ventilation, and vital status.

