7.1 Participant withdrawal criteria

Participants may be terminated early from the study for the following reasons:

- a. The participant elects to withdraw consent from study activities.
- b. The participant dies.
- c. The participant has a serious allergic or anaphylactic reaction to the study drug
- d. The participant's condition deteriorates significantly necessitating either a transfer to the intensive care unit (ICU) or the need for advanced respiratory support (high flow oxygen ≥ 15 L/minute, CPAP, non-invasive or invasive mechanical ventilation), and the treating clinician thinks it is in the best interest of the patient to be withdrawn \pm unblinded. If the patient is unblinded, any open label use of sirolimus after that will be based on clinical grounds at the discretion of the treating clinician(s). The study drug (sirolimus or placebo) will continue for the maximum stipulated duration of 14 days regardless of escalation in care, unless the patient is withdrawn from the study.
- e. In the opinion of the investigator, it is not in the participant's best medical interest to continue to participate in the study.

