8.5 Other study parameters

Daily chart reviews will be performed to record other variables of interest:

Need for advanced respiratory support: Recorded as Yes/No and type, whether high flow oxygen \geq 15 liters/minute, CPAP, non-invasive, or invasive mechanical ventilation. If a patient receives more than one form of advanced respiratory support in the same day, (e.g. started on non-invasive and worsens to require invasive ventilation, or extubated from invasive to non-invasive ventilation), we will designate the most advanced form of ventilation (in the above scenarios – mechanical ventilation) for that day. The ranking order for the above modes of respiratory support are (from most advanced to least advanced means): 1. Mechanical ventilation, 2. Non-invasive ventilation (e.g. bilevel), 3. CPAP, 4. High flow supplemental oxygen \geq 15 L/minute. Of note, the use of CPAP employed to treat pre-existing obstructive sleep apnea will not count as advanced respiratory support.

Duration of advanced respiratory support: For patients who progress to require advanced respiratory support, the type(s) of support and the time spent on the support (individual modes as well as cumulative, days) will be recorded.

Vital status: The vital status (alive/deceased) will be recorded at study termination as well as at the time of hospital discharge (in case that happens after the 14-day study period). For non-survivors, the time from study initiation to death will also be recorded.

Duration of hospital stay (days): will be recorded starting from the day of admission to the day of hospital discharge. This parameter will only be used for analysis in patients who survive the hospital stay.

9. Risks

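### AE and SAE collection stops when treatment stops, so new non-fatal events in the following days, while drug is still present, are not routinely collected

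*Combined protocol and SAP*

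**What the plan says.** Section 14.4.1 gives AEs and SAEs one collection period, beginning "when the consent form is signed and will continue until the end of the treatment". Section 6.1 fixes the end of treatment: "Patients will be on the study drug for a maximum duration of 14 days, or until hospital discharge, whatever happens first". The synopsis agrees: "for a maximum treatment duration of 14 days or until hospital discharge, whichever happens sooner". A patient discharged on day 5 therefore has a safety window of about five days. Section 6.2, footnote 6, treats the last hospital day as day 14 for study assessments.

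Two other places point the same way. Section 14.3.1 defines an AE as something experienced during trial participation, and Section 7.2 caps participation at 14 days.

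Section 4.3 lists among the key secondary endpoints "Drug safety profile (Incidence and type of adverse and serious adverse events". Section 9.1 singles out secondary infections, pneumonitis, creatinine rises and falling blood counts as the side effects of particular interest.

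Some information is collected later:
- Section 6.2, footnote 7: "Long term outcomes following the 14-day study period will be assessed by chart reviews".
- Section 6.3, for stays longer than 14 days: staff will "record key variables such as the need for advanced respiratory support, duration of hospitalization, duration of ICU status", plus ventilation time and vital status.
- Section 8.5: "The vital status (alive/deceased) will be recorded at study termination as well as at the time of hospital discharge".
- Sections 13.1.2 and 14.5 follow AEs already present.
- Section 13.2 follows patients taken off drug because of an AE.
- Section 14.3.5 counts as an SAE a death learned of in a protocol-defined follow-up.
- Section 6.6 allows later record review if the patient opts in.

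**The concern.** The trial's safety result is a table of AEs and SAEs by arm, meant to inform a larger trial. Under Section 14.4.1 the table stops at the last day of treatment, although sirolimus is eliminated slowly. A patient who goes home and is readmitted two days later with pneumonia or pneumonitis has had an event of the kind Section 9.1 wants to detect, yet nothing in the plan requires it to be recorded as an AE or SAE. The same applies to a patient withdrawn for a reason other than an AE. It also matters for patients unblinded after deterioration, because Section 7.1 says: "If the patient is unblinded, any open label use of sirolimus after that will be based on clinical grounds". Events during such use would not necessarily be collected, or be separated from events on blinded drug.

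**Working it through.** **What is collected after treatment ends**

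| Provision | Who is covered | New non-fatal AEs/SAEs? |
|---|---|---|
| 13.1.2, 14.5 | Patients with an existing AE | No; the existing event is followed |
| 13.2 | Patients withdrawn from drug because of an AE | May surface; can end at discharge, at resolution or stabilisation, or when the investigator decides |
| 6.3 | Patients still in hospital after day 14 | Respiratory support, ICU and ventilation time, vital status; the list is open-ended but does not name AEs |
| 8.5 | Patients discharged after day 14 | Vital status only |
| 6.2, footnote 7 | Not limited to a subgroup | Long-term outcomes; no content or end date given |
| 14.3.5 | Not limited to a subgroup | Deaths only; the follow-up is not defined for AEs |
| 6.6 | Patients who opt in | Record review, not described as AE reporting |

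The AE review row in Section 6.2 has no mark under F/u. That is weak evidence by itself, because in the text available no row has a mark in that column. Section 14.4.1 is what sets the limit.

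**Is drug still present when collection ends?**

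The plan states no figure for this, so there is none to reproduce.

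Input: terminal half-life *h* = 62 ± 16 h (Section 11.2, stable renal transplant patients). One SD either side gives 62 − 16 = 46 h and 62 + 16 = 78 h.

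Assumption: one compartment with first-order elimination. The fraction of the amount at last dose that remains after *t* hours is 0.5^(*t*/*h*). It does not depend on the loading dose or the length of the course.

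- 3 days (72 h): 0.5^(72/62) = 0.447; 0.338 at 46 h; 0.527 at 78 h. About 45% (34–53%).
- 7 days (168 h): 0.5^(168/62) = 0.153; 0.080 at 46 h; 0.2247 at 78 h. About 15% (8–22%).

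**How far would a fixed day 28 reach?**

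After a last dose on day 14, day 28 is 14 × 24 = 336 h later.

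- 336/62 = 5.4 half-lives, with about 2% remaining.
- 336/78 = 4.3 half-lives, with about 5% remaining.

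Patients who stop earlier are covered for longer after their last dose.

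**The case against.** The strongest reply is that the plan is not blind after treatment ends. Deaths, new respiratory support and ICU time are recorded for patients still in hospital. AE-related withdrawals have safety follow-up that is not worded as limited to the original event. Chart review continues in some form. All of this stands, and it rules out several broader readings:

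- *No safety information is collected after treatment.* A reader might infer this from Section 14.4.1 alone. Sections 6.3, 8.5, 13.2 and 14.3.5 show otherwise.
- *All withdrawn patients are lost to safety follow-up.* Section 13.2 covers those withdrawn because of an AE. The gap concerns other withdrawals.
- *Late serious events escape oversight.* The suspension rules (7.2, 13.1.3) and FDA reporting rules (14.8.2) carry no time limit, and the clocks in 14.8.1 and 14.10.4 run from learning of the event. The gap lies in whether anyone looks, and so in the tabulated safety data.
- *Windows that depend on discharge bias the comparison of arms.* The documents give no lengths of stay or event rates by arm, so neither a direction nor a size can be established.
- *Section 14.3.5 flatly contradicts 14.4.1.* It refers to a follow-up that is not defined for AEs. That wording needs aligning and falls short of a clear contradiction.

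It is also fair to say that residual drug is not evidence of harm, that the half-life may differ in patients with COVID-19, and that this is a 30-patient pilot with a descriptive safety table. These points limit the weight of the concern. They do not supply the missing collection.

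**Conclusion.** The point holds in this form: after day 14 or earlier discharge, there is no routine collection of new non-fatal AEs or SAEs. The gap is widest after discharge and after withdrawal for reasons other than an AE. The key secondary safety endpoint closes with roughly 45% of the amount at last dose still present three days later and 15% at seven days, given the protocol's half-life and first-order elimination. The number of events this would miss cannot be estimated from the documents. It is a worthwhile and inexpensive improvement; it does not undermine the trial or its efficacy analysis.

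**What to change.** Amend Section 14.4.1 so that AE and SAE collection runs from consent to one fixed study day for every dosed patient, regardless of discharge or early stop, unless the patient withdraws consent to further data collection. Day 28 is one workable example; the choice is a convention, since the documents set no washout standard. Collect by chart review plus one telephone contact, and mark this under F/u in Section 6.2.

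Report AE and SAE incidence by arm over that common window, alongside on-treatment incidence, and flag events that start after any open-label sirolimus.

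Reconcile the wording of Sections 6.2 (footnote 7), 7.2, 13.2, 14.3.1, 14.3.5 and 14.4.1, so that participation, follow-up and the AE period mean the same thing throughout.

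Cost: a short amendment, a consent form update with IRB approval (Section 17.2), and at most about 30 calls. Dosing and the efficacy analysis do not change. The main limitation is that ascertainment after discharge, especially of mild and laboratory events, will be less sensitive than daily inpatient chart review with scheduled tests. A common window equalises calendar time but not detection, and the report should say so.
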